3.5 Secondary Study Endpoints

The secondary endpoints will be the amount of medication administered via the patient-controlled function on the adductor catheter as well as duration of narcotic use required in each cohort. We hypothesize that the intermittent bolus cohort will require fewer doses of patient-administered medication and will use narcotic medication for a shorter duration when compared to the continuous infusion and placebo groups.

We will additionally calculate the overall morphine equivalents used in each cohort during their hospitalization, and dividing this by the total number of post-surgical hospitalization hours in order to normalize the data.

Nausea and vomiting will be recorded daily using the postoperative nausea and vomiting scale and compared between groups. Presence of constipation will be a subjective rating by the patient that is also recorded daily. We will compare the post-surgery length of hospitalization between groups. Finally, we will compare patient-reported outcomes using the KOOS Jr. questionnaire.

We hypothesize that the intermittent bolus cohort will use less narcotic mediation and will therefore have lower rates of constipation, nausea and vomiting. Furthermore, we believe this cohort will demonstrate equivalent lengths of stay and patient-reported outcomes as compared to the comparison groups.

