7.1 Sample Size Determination

Twenty eight patients will be recruited into each arm, for a total of 84 patients. This number has been chosen for feasibility rather than based on a formal power analysis. We will use this study to provide data for a formal power analysis in order to power a larger study.

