7.2 Statistical Methods

Descriptive and Inferential Statistics

Continuous variables will be summarized with the sample mean, median, standard deviation, minimum, 25th percentile, 75th percentile, and maximum. Categorical variables will be summarized with number and percentage of patients. All analysis will be performed on the basis of the intention-to-treat principle. Comparisons of endpoints between the three treatment arms will be made using a Wilcoxon rank sum test (continuous or ordinal endpoints) or Fisher's exact test (categorical endpoints). Missing data will be imputed using either the last observation carried forward method, a regression-based approach, or another method, depending on the extent of missing data. In order to adjust for the three pair-wise comparisons between treatment groups that will be made for each endpoint, we will utilize a Bonferroni correction for multiple testing, after which p-values of < 0.0167 will be considered as statistically significant. All statistical tests will be two-sided.

Primary Hypothesis:

We hypothesize that the intermittent bolus infusion cohort will report improved pain scores compared to continuous infusion catheters and placebo cohorts.

Secondary Hypothesis:

We hypothesize that the intermittent bolus cohort will require fewer doses of patient-administered medication and will use narcotic medication for a shorter duration when compared to the continuous infusion and placebo groups.

Interim Analysis

We will evaluate the first twenty patients. If 50% of the patients are withdrawn from the study for poor pain control or serious adverse reactions to the study medication, then we will close the study early.

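### Section 3.5 anticipates equivalent length of stay and patient-reported outcomes, but the difference tests planned in section 7.2 could not support an equivalence conclusion

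*Combined protocol and SAP*

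**What the plan says.** Section 3.5 lists two outcomes for comparison: "We will compare the post-surgery length of hospitalization between groups", and "we will compare patient-reported outcomes using the KOOS Jr. questionnaire". The section closes with the expected result for the bolus arm against the other groups: "we believe this cohort will demonstrate equivalent lengths of stay and patient-reported outcomes". Section 3.3 places the postoperative KOOS Jr. questionnaires at 30 and 60 days.

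The inferential method is in section 7.2: "Comparisons of endpoints between the three treatment arms will be made using a Wilcoxon rank sum test (continuous or ordinal endpoints"), with Fisher's exact test for categorical endpoints. Also, "All statistical tests will be two-sided". The Bonferroni step covers the three pairwise comparisons per endpoint, "after which p-values of < 0.0167 will be considered as statistically significant".

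On size, section 7.1 says "Twenty eight patients will be recruited into each arm, for a total of 84 patients", and "This number has been chosen for feasibility rather than based on a formal power analysis".

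No section gives an equivalence margin, an equivalence procedure or a confidence interval for any between-arm difference. The summaries listed in 7.2 are descriptive. Section 3.4 plans a mean difference for pain only, without an interval.

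**The concern.** A test of difference can give evidence that two arms differ. If it does not reach significance, that alone is not evidence that they are alike: the same result arises when the arms are close and when the sample is too small to separate them. To conclude equivalence, one needs an interval for the difference that is narrow relative to a difference that would matter. The plan names the conclusion it expects but specifies neither the interval nor the difference.

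At stake is what may be said about length of stay and function at the end of the trial. If the bolus mode carried a moderate disadvantage on either outcome, the planned tests would often miss it, and nothing in the planned output would show the reader how large a disadvantage remained compatible with the data.

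**Working it through.** **Inputs from the documents.** 28 per arm, 84 in total (7.1); two-sided tests at 0.0167 (7.2).

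**Assumptions.** The documents give no SD, relevant difference or margin for either outcome, so everything below is in SD units over a range of true differences. The calculations take normal data with equal variances and all 28 patients per arm observed.

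**Step 1: the plan's own figures.** 0.05 / 3 = 0.01667, which rounds to 0.0167. 3 × 28 = 84. Both reproduce. There is no power calculation to reproduce.

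**Step 2: precision of a pairwise difference.** The standard error in SD units is √(2/28) = 0.267. The two-sided level 0.0167 corresponds to a 98.3% interval, with half-width t(0.99167; 54 df) × 0.267 = 2.471 × 0.267 = 0.66 SD. The normal approximation gives 2.394 × 0.267 = 0.64 SD. So with an observed difference of exactly zero, the interval still runs from −0.66 to +0.66 SD. A difference just short of significance would have an interval from about 0 to 2 × 0.66 = 1.32 SD.

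**Step 3: chance of a non-significant result when a real difference exists.** The noncentrality parameter is d / 0.267. The last two columns give the probability of p ≥ 0.0167 for one pairwise comparison. The t-test figures come from the noncentral t distribution with 54 df; the Wilcoxon figures come from 20,000 simulated trials.

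| True difference d | Noncentrality | t-test | Wilcoxon, simulated |
|---|---|---|---|
| 0.3 SD | 1.12 | 90% | 91% |
| 0.5 SD | 1.87 | 72% | 74% |
| 0.8 SD | 2.99 | 30% | 34% |

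The sentence in 3.5 refers to both comparison groups. If the bolus arm differed by 0.5 SD from each of them in the same direction, both Wilcoxon tests were non-significant in 61% of simulated trials.

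**Step 4: effect of the Bonferroni threshold.** At 0.05 instead of 0.0167, the non-significance probability at 0.5 SD falls to 55% (t-test) or 57% (Wilcoxon). The correction guards against false claims of difference, but it makes a non-significant result more common and so less informative.

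**Step 5: what a formal equivalence analysis could show at this size.** Take two one-sided tests at 0.05, a true difference of zero and the normal approximation. The smallest margin with 80% power is (1.645 + 1.282) × 0.267 = 0.78 SD. A margin of 0.5 SD would have 18% power with 28 per arm and would need 69 per arm for 80% power.

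**The case against.** A reader might infer that the plan will declare equivalence whenever p ≥ 0.0167. The documents do not support that. Section 7.2 says when a p-value counts as significant and assigns no meaning to a larger one, and no other section supplies such a rule. What can be said is narrower: the plan provides no other basis for the claim in 3.5.

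A reader might also take equivalence to be one of the trial's formal hypotheses. It is not. The sentence is worded as a belief, directly after a hypothesis about narcotic use and side effects. The primary and secondary hypotheses in 7.2 omit it, and neither outcome appears in the aims or in the section 2 objectives. An informal expectation of no difference is a fair reading. Still, the sentence predicts what the cohort will demonstrate on two outcomes listed for comparison, so it states an expected conclusion.

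Three further points on the other side have some force:

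- Sections 3.2 and 7.1 describe a pilot sized for feasibility, and no decision in the plan depends on an equivalence finding. This limits the harm. It does not make the claim supportable, because a study of this size is poorly placed to show equivalence.
- The absence of intervals applies to every endpoint, and a reader could build an approximate one from the means and SDs if these are given by arm. That is true, but this is where an interval is most needed, because the expected conclusion is about similarity.
- The tests are two-sided, so a clear loss in the bolus arm could be detected as well as a gain. That stands; the table shows how large such a loss would have to be.

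**Conclusion.** The concern holds as a mismatch between the conclusion anticipated in 3.5 and the analysis in 7.2: the planned tests could not support equivalence for length of stay or KOOS Jr. With 28 per arm, a non-significant result would be compatible with differences of two thirds of an SD or more. It would occur in about 90%, 72–74% and 30–34% of trials if the true difference were 0.3, 0.5 and 0.8 SD respectively.

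These figures rest on normality and complete data. Length of stay may fit a normal model poorly, and any withdrawals would widen the intervals further. The choice among 0.3, 0.5 and 0.8 SD is illustrative, since the documents do not say what difference would matter.

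Severity is low. These are further secondary outcomes outside the formal hypotheses of a feasibility-sized pilot, and the primary pain comparison asks about a difference and is unaffected.

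**What to change.** In section 3.5, replace the wording about demonstrating equivalence with a statement that no difference is expected in length of stay or KOOS Jr.

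In section 7.2, add two items:

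1. For length of stay, and for KOOS Jr. at 30 days and at 60 days, report each pairwise between-arm difference with its 98.3% confidence interval. One estimate is enough; the Hodges–Lehmann shift would match the Wilcoxon test.
2. State that a non-significant result will not be interpreted as equivalence.

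No margin is needed if equivalence is not claimed. If the sponsor wishes to keep the claim, a justified margin for each outcome and KOOS Jr. time point would have to be set in advance, accepting that 28 per arm gives 80% power only for margins near 0.8 SD.

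The cost is a little more analysis work and a slightly less favourable conclusion. No extra patients or data are required. Estimates with intervals would also serve the purpose stated in 7.1, which is to inform the power analysis of a larger study.

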3.6 Primary Safety Endpoints

If patients report serious adverse side effects from a medication in the multi-modal regimen, or if they report uncontrolled pain, they will be withdrawn from the study and provided alternative medication per the treating surgeon's discretion.

3.7 Identification of Source Data

The following source data will be directly recorded on the Case Report Form (CRF) at the pre-op visit and inputted into REDcap, a password protected database.

- Name
- Medical Record Number
- Email address
- Date of Birth, Age
- Gender
- Race
- Weight (lbs), Height (In), BMI
- Previous surgeries? (yes, no)
- Are you taking Nsaids? (yes, no)
- Previous injections (yes, no)
- Baseline NRS score
- Laterality of surgery
- KOOS Jr. Questionnaire
- Device serial number

The following source data will be recorded daily for two weeks using an online questionnaire recorded into REDcap, and continued weekly until discontinuation of narcotic medication. This data will again be collected at 30 and 60 days following the date of surgery.

- Name
- Medical Record Number
- Date of Birth
- How long has it been since your operation? (Less than 1 month, 1-2 months, Greater than 2 months)
- Are you using narcotic medication? (yes/no)
 - What was the date you last consumed narcotic medication? (if no to previous answer)
- How would you rate the pain you have been experiencing? (0-10)

- Have you been experiencing constipation over the past 24 hours? (yes, no)
- Have you been vomiting or had dry-retching over the past 24 hours? (once, twice, three or more times, no)
- Have you been experiencing a feeling of nausea (an unsettled feeling in the stomach and slight urge to vomit) over the past 24 hours? (yes, no)
- KOOS Jr. Questionnaire (only recorded during 1 month and 2 month questionnaires)
- Rate of on-demand catheter use (recorded at final survey only)

4 Subject Selection Enrollment and Withdrawal

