1.3 Clinical Data to Date

Research has focused on prescribing practices, demonstrating the risks of long-term opioid use with large initial prescriptions.^{5,8,20} This has led hospitals to develop institutional guidelines to reduce excessive prescriptions of narcotics following routine surgical procedures. For example, Wyles et al. demonstrated a reduction in the average oral morphine equivalents (OMEs) prescribed at discharge from 750 to 388 following total joint arthroplasty, after departmental adoption of standard prescribing guidelines. Interestingly, the authors reported no increase in refill rates, suggesting that the change largely reduced the amount of unused medication.²¹

At our own center we reported that the number of OMEs prescribed at discharge was not predictive of patients requesting a refill of their medication. We instead found that patients with lower pain scores on postoperative day #1, but not postoperative day #2, had a lower risk of requiring a refill of their pain medication.¹¹ We hypothesized that patients who developed an early reliance on narcotics would be harder to wean from the medication and be at a greater risk of long-term opioid use. Due to this we began to utilize an adductor canal pain catheter for total knee arthroplasty patients to provide improved pain control early in the postoperative period. Following adoption of the adductor canal catheter we reported a subsequent 43% decrease with in-hospital narcotic use.¹⁰ Building upon this we then completed a prospective, randomized, double-blinded, placebo-controlled trial comparing our multimodal regimen with and without schedule II narcotics (oxycodone). In that study we demonstrated equivalent pain scores between the narcotic and placebo group when using a continuous infusion adductor canal pain catheter. The narcotic group, however, had a higher proportion of patients that required pain medication at 60 days postoperatively (*submitted for publication*).

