1.5 Risks and Benefits

The benefits of the study will be to evaluate the efficacy of the differing modes of medication delivery through the adductor canal pain catheter. If optimized, we believe this will allow us to continue to reduce the amount of narcotic medications prescribed following orthopedic surgery.

All components of the multimodal pain regimen are currently safely used in orthopedic patients. There is a theoretical risk of renal damage or GI upset with the use of anti-inflammatory medications, but we have not seen this with our total knee study. There is also the possibility that patients will have uncontrolled pain following surgery. These patients will have IV narcotic medication as a safety net during their hospitalization and will be able to utilize our standard opioid regimen upon discharge.

2 Study Objectives

Primary Objective

The primary objective will be to compare postoperative pain levels between the treatment groups, using the Numerical Rating Scale (NRS).

Secondary Objective

The secondary objectives will be to compare the amount of patient-administered medication use between groups as well as duration of narcotic use between groups.

3 Study Design

This project will be conducted as a three-arm double-blinded, randomized controlled trial comparing differing modes of medication dispersion using the adductor canal pain catheters. The three arms will be a single shot adductor canal block (with saline filled catheter) compared to ropivacaine 0.2% continuous infusion, and ropivacaine 0.2% intermittent bolus infusions. Treatment groups will be assigned to patients using computer-based randomization via the dynamic allocation method of Pocock and Simon. Subjects will be screened in the outpatient clinic setting and those interested and eligible will be consented and enrolled in the trial.

A total of 84 patients will be enrolled in this study. Twenty eight patients will be in each comparison group. After enrollment patients will undergo randomization by the research pharmacy in order to maintain blinding of the surgical team, nursing staff, and patient. The patient will then undergo their surgical procedure and receive a multi-modal pain regimen as described below. All treatment groups will receive the same regimen with the exception of the adductor canal catheter. All of the patients will have the catheter placed in the Post Anesthesia Care Unit following

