3.1 General Description

Patients will receive the following multi-modal pain regimen in addition to the adductor canal pain catheter.

Preoperative (All patients receive the following in the pre-op holding):

Acetaminophen 1000 mg oral

Celebrex 400 mg oral

Dexamethasone 10 mg IV

Intraoperative (All patients receive the following):

Periarticular block

- Ketorolac 30 mg with weight-based ropivacaine and epinephrine, diluted in normal saline to a total volume of 120 mL (50-74.9 kg – ropivacaine 200 mg, epinephrine 0.1 mg), (75 – 99.9 kg – ropivacaine 300 mg, epinephrine 0.2 mg), (100 kg and greater – ropivacaine 400 mg , epinephrine 0.3 mg).

Postoperative:**Adductor canal pain catheter (saline or ropivacaine)**

Acetaminophen 1000 mg oral every 6 hours scheduled

Tramadol 50 mg oral every 6 hours as needed

Dexamethasone 10 mg IV scheduled daily while hospitalized (*max 3 days*)

Toradol 10 mg oral every 6 hours scheduled daily while hospitalized (*max 3 days*)

Oxycodone 5 mg every 3 hours as needed for pain

Dilaudid 0.5 mg IV push every 3 hours as needed for pain > 8 on VAS score

Discharge:

Acetaminophen 1000 mg oral every 6 hours scheduled (x2 weeks)

Tramadol 50 mg oral every 6 hours as needed for pain

Celebrex 400 mg oral scheduled daily (x2 weeks)

Oxycodone 5 mg every 3 hours as needed for pain

[figure not shown]
At the time of discharge, medications will be filled for two weeks. Patients will report their pain scores during this time via electronic and phone surveys. If additional pain medications are required these will be filled per the treating physician's discretion.

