5.6 Prior and Concomitant Therapy

If a patient has taken a narcotic medication (schedule II) in the 3 months leading up to surgery they will be excluded from the study. Patients may request and be provided refills for narcotic medication at the discretion of the treating surgeon.

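### Aim 3 (duration of narcotic use) rests on survey items that name no drug, and the protocol never says whether tramadol counts

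*Combined protocol and SAP*

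**What the plan says.** The Study Summary lists comparison of the duration of narcotic use as Aim 3. Section 3.5 makes "duration of narcotic use required in each cohort" a secondary endpoint, and section 7.2 attaches a hypothesis to it: shorter use in the intermittent bolus arm.

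The data for it are in section 3.7. The patient is asked "Are you using narcotic medication? (yes/no" and, after a no, "What was the date you last consumed narcotic medication? (if no to previous answer". These items are completed daily for two weeks, then weekly until narcotics are discontinued, and again at 30 and 60 days.

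The discharge list in section 3.1 contains both "Tramadol 50 mg oral every 6 hours as needed for pain" and "Oxycodone 5 mg every 3 hours as needed for pain". Both drugs are also on the in-hospital list. Section 3 (Study Design) states that "All treatment groups will receive the same regimen with the exception of the adductor canal catheter", so this applies to all three arms. Sections 3.1 and 5.6 also allow further pain medication or refills at the treating clinician's discretion.

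The protocol's use of the word narcotic varies. Section 5.6, on prior therapy, begins "If a patient has taken a narcotic medication (schedule II) in the 3 months leading up to surgery". Section 1.3 describes an earlier trial "with and without schedule II narcotics (oxycodone". Section 5.5, on follow-up after discharge, continues the weekly questionnaires until every narcotic has been stopped, without listing any.

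**The concern.** The endpoint, the survey item and the rule for ending the weekly surveys all depend on one undefined word, while every patient is prescribed two drugs to which it may or may not apply. No drug name is recorded after discharge, so the analyst cannot recover which drug an answer referred to. The in-hospital morphine equivalents in section 3.5 stop at discharge and do not help.

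Three things are at stake. The first is the meaning of the Aim 3 result: time to the last oxycodone dose, time to the last dose of either drug, or a mixture. The second is its precision. The third is the use of the trial for planning: section 7.1 says its data will feed a formal power analysis for a larger study, and if duration is among the endpoints considered, its standard deviation would come from mixed definitions.

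**Working it through.** No figure in the plan rests on this point, so the check is mainly a comparison of texts.

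**1. What each reading gives**

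| Patient's current use | Answer if only oxycodone counts | Answer if either drug counts |
|---|---|---|
| Oxycodone, with or without tramadol | yes | yes |
| Tramadol alone | no | yes |
| Neither | no | no |

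The readings differ only for patients on tramadol alone. Both drugs are prescribed as needed, so some patients may take one or neither. The documents do not say how many pass through a tramadol-only phase or how long it lasts.

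**2. Does another section settle it?**

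- Section 5.6 pairs narcotic with schedule II, but it concerns use before surgery.
- Section 1.3 gives oxycodone as the schedule II drug, but for an earlier trial.
- Section 5.5 concerns the right period and leans towards the broad reading, but it lists no drugs and does not mention tramadol.
- Sections 3.5 and 7.2 name the endpoint without defining the word.
- Section 3.7 explains nausea in lay terms and gives constipation, vomiting and nausea a 24-hour window. The narcotic item has neither an explanation nor a window.

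None of these carries a definition into the endpoint or the survey.

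**3. Effect on the comparison**

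Let a share f of patients answer for oxycodone only and the rest for either drug, with f the same in every arm and unrelated to a patient's own duration. The expected difference between two arms is then

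f × (difference in oxycodone duration) + (1 − f) × (difference in either-drug duration).

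This is a blend of two estimands, not a value pulled towards zero. If the two stop dates differ by a constant g, the variance rises by f(1 − f)g². The standardised difference shrinks, and so does the power of a rank comparison.

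**4. Illustration only**

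From the plan: 28 per arm (3 × 28 = 84) and a two-sided threshold of 0.05/3 = 0.0167 for each pairwise comparison. Assumed: f of 25% or 50%, g of 0.5 to 1.5 standard deviations (SD), the same true difference under both definitions, and a normal approximation in place of the planned Wilcoxon test.

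- Difference giving 80% power without mixing: (2.394 + 0.842) × √(2/28) = 0.865 SD.
- Inflated SD: √(1 + f(1 − f)g²). For f = 0.5 and g = 1 this is √1.25 = 1.118.
- Power for the same difference: Φ(0.865 / (1.118 × √(2/28)) − 2.394) = Φ(0.50) = 69%.

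| g (SD) | Power, f = 25% | Power, f = 50% |
|---|---|---|
| 0.5 | 78% | 77% |
| 1.0 | 72% | 69% |
| 1.5 | 63% | 58% |

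The loss runs from minor to substantial, depending on inputs that the documents do not give.

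**5. Effect on follow-up**

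Daily surveys run to day 14 whatever the answer. Only the weekly surveys stop on a no, and the same items return at days 30 and 60. The Study Summary sets participation at 60 days or narcotic discontinuation, whichever is later. What can be lost is weekly detail between those contacts, and follow-up past day 60 for a patient still on a drug that he or she did not count.

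**The case against.** **The actual questionnaire may name the drugs.** Section 3.7 is a list of source data and is not shown to be the final form, and staff telephone patients who miss a survey. This is possible. But the section gives the items as worded to the patient, with response options, and no drug list or telephone script appears anywhere. If such a list exists, the protocol should cite it.

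**The protocol already leans to the broad meaning.** A reader might infer that it uses narcotic for schedule II drugs and so contradicts itself. The documents do not support that. In sections 1.3 and 4.2, schedule II qualifies a wider noun; only section 5.6 comes close to equating the two, and it concerns eligibility. Section 5.5 favours the broad reading. This stands, but section 5.5 neither mentions tramadol nor reaches the patient.

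**Follow-up is not cut off.** A reader might infer that a mistaken no ends follow-up. It does not, because of the surveys at days 30 and 60. This stands and narrows the loss. Those surveys use the same undefined word, however, and rely on longer recall.

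**No bias is shown.** A reader might also infer that arm differences are biased, either towards zero or between arms. Noise unrelated to arm lowers precision and leaves the raw mean difference a blend. Bias between arms would require the share of tramadol-only patients to differ by arm. That is possible if one catheter mode changes the mix of drugs taken, but nothing in the documents shows it, and the wording is the same in all arms.

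**The stakes are modest.** This is a secondary endpoint in a trial sized for feasibility. Pain scores and pump demand use are measured separately. This stands, and it is why the point is an improvement and not a fault that threatens the trial.

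**Conclusion.** The point holds as a gap in definition and measurement. Followed as written, section 3.7 yields durations that mix two definitions, and the data collected cannot separate them. The consequences are lower precision, an Aim 3 result that is hard to interpret, a possibly inflated SD for planning the larger study, and some loss of weekly detail or of follow-up past day 60.

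No size can be given from the documents. They contain no SD for duration, no share of patients on tramadol alone and no length for that phase. The power figures of 58% to 78% against a nominal 80% are illustrative and rest wholly on the assumed share and gap. The conclusion itself needs only that some patients take tramadol after their last oxycodone dose and that they do not all read the word alike.

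This is a cheap improvement, best made before data collection, because the drug behind each answer cannot reliably be recovered later.

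**What to change.** - **Section 3.7:** replace the single item with separate lines for oxycodone, tramadol and any other prescribed opioid. Each asks whether the drug was taken since the last survey and the date of the last dose. A since-last-survey window suits as-needed drugs. A 24-hour window on a weekly survey would record a no for someone taking a dose every few days.
- **Section 3.5:** state which drugs define the Aim 3 duration, and report the other definition as secondary.
- **Sections 3, 3.3, 5.5 and 6.4:** continue the weekly surveys until no listed drug has been taken since the previous survey.
- **Telephone contacts:** use the same wording.

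The cost is an edit to the REDCap form, short text changes in the protocol and a slightly longer survey. No change to treatment is involved.

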3.4 Primary Study Endpoints

The primary endpoint will be pain scores, calculated by the Numerical Rating Scale. This score will be collected daily during the hospital examination and by online or phone surveys after discharge. We will calculate the mean difference in recorded pain scores between cohorts. We hypothesize that the intermittent bolus infusion cohort will report improved pain scores compared to continuous infusion catheters.

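### The primary pain question has no recall period and does not say current, average or worst pain, although the side-effect questions beside it are anchored to 24 hours

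*Combined protocol and SAP*

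**What the plan says.** Section 3.4 defines the primary endpoint: "The primary endpoint will be pain scores, calculated by the Numerical Rating Scale". On its source it says: "This score will be collected daily during the hospital examination and by online or phone surveys after discharge". On its analysis: "We will calculate the mean difference in recorded pain scores between cohorts".

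The question itself is in section 3.7: "How would you rate the pain you have been experiencing? (0-10". Two of the three symptom questions beside it read "Have you been experiencing constipation over the past 24 hours? (yes, no" and "Have you been vomiting or had dry-retching over the past 24 hours". The nausea question ends in the same way: "an unsettled feeling in the stomach and slight urge to vomit) over the past 24 hours? (yes, no". The preoperative value is listed only as "Baseline NRS score".

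Sections 3 and 3.7 use this questionnaire daily for 14 days, then weekly until narcotics are stopped, and again at days 30 and 60. Section 3 sends it in the morning, with staff contact if it is not completed by the afternoon. Section 6.3 says that pain is recorded daily in hospital but gives no question wording. Section 7.1 says that the sample size was chosen for feasibility and that the data will feed a power analysis for a larger study.

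**The concern.** The secondary symptoms are defined more tightly than the primary endpoint. The phrasing of the pain question can fairly be read as pain now, since the last survey, over the past day or since surgery, and as typical or worst pain. The plausible period widens with the survey interval, from a day in the first two weeks to a week at the weekly surveys and longer at days 30 and 60. A patient who rates current pain is also measured at a varying time of day, since late responders are contacted later than those who answer in the morning.

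If patients settle on different readings, the differences between readings become part of the between-patient variance. With 28 per arm and a per-comparison threshold of 0.0167, the trial has little room for that. An inflated SD would also pass into the planning of the larger trial. An answer given to an unanchored question cannot be re-anchored afterwards.

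**Working it through.** **The plan's own figures.** 3 × 28 = 84 and 0.05 / 3 = 0.0167; both reproduce. The plan gives no SD, effect size, power or reliability, so everything below rests on assumed inputs.

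**Is an anchor given elsewhere?**

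| Place | What it gives for pain |
|---|---|
| 2, 3.4, 7.2 | NRS or pain scores; no period, no pain type |
| 3 | Survey schedule and time of day only |
| 3.7, preoperative list | Baseline NRS, no period |
| 3.7, survey list | The question with a 0–10 scale, no period, no pain type |
| 6.3 | Daily in-hospital recording, no wording |

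No section supplies the missing definition.

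**Loss for one score.** Assume that the ambiguity lowers the reliability of a single score from 0.90 to 0.80.
- Standardised effect is multiplied by √(0.80 / 0.90) = 0.943, so it shrinks by about 6%.
- Effective sample is multiplied by 0.80 / 0.90 = 0.889, a loss of about 11%; 0.111 × 28 = 3.1 patients per arm.
- Variance is multiplied by 0.90 / 0.80 = 1.125. A larger trial planned from this SD would be 12.5% bigger than one planned on the sharper item, for the same target difference.

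**Loss for a mean of k daily scores with independent errors.** Spearman–Brown: R = k·r / (1 + (k − 1)·r).
- k = 4: 3.6 / 3.7 = 0.973 and 3.2 / 3.4 = 0.941. Ratio 0.967, a loss of about 3% (0.033 × 28 = 0.9 patients per arm).
- k = 14: 12.6 / 12.7 = 0.992 and 11.2 / 11.4 = 0.982. Ratio 0.990, a loss of about 1%.

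If each patient keeps to one reading of the question, the errors are shared across days and averaging does not remove them. With wholly shared errors the loss stays at 11% for any k.

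**Range over the assumption.** Let inconsistent reading make up a share f of the total score variance (the case above is f = 0.111). Take the difference that would have 80% power without it: (2.394 + 0.842) × √(2 / 28) = 0.86 SD, by the normal approximation with two-sided alpha 0.0167. Power is then Φ(3.236 × √(1 − f) − 2.394).

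| f | Effective n per arm, 28 × (1 − f) | Power |
|---|---|---|
| 0 | 28.0 | 80% |
| 0.10 | 25.2 | 75% |
| 0.20 | 22.4 | 69% |
| 0.30 | 19.6 | 62% |

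The 80% is a reference point for the illustration, not a target in the plan.

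**The case against.** During the first 14 days the question is asked every day, usually in the morning, next to three questions with a 24-hour window. Many patients will take it to mean the time since the last survey. The ambiguity is therefore narrower in the early period than at the weekly, day-30 and day-60 surveys. That stands, and it limits the size of the effect. It does not settle whether average, worst or current pain is meant. Nor can the missing window be put down to an abbreviated list, because the same list keeps the window for the other three symptoms.

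The trial is described as a feasibility-sized pilot, so a modest loss of precision breaches no stated power target. That also stands. But a pilot whose purpose includes supplying an SD has its own reason to measure the primary variable cleanly.

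A reader might infer more: that hospital and survey scores are pooled, that the endpoint therefore mixes different pain constructs, and that arms with different lengths of stay would be biased against each other. The documents do not support this.
- Section 3.4 gives no time point or rule for combining scores, so pooling is one reading and not stated text.
- The in-hospital wording is absent. Sections 3 and 3.7 describe one daily questionnaire for two weeks without excepting hospital days, and section 6.3 speaks of the same values continuing after discharge. One item throughout is possible.
- Bias would need both a different in-hospital measure and a difference in stay between arms. Section 3.5 hypothesises equivalent stays. Even an assumed 1-point offset with a half-day difference in stay moves a 4-day mean by 0.5 / 4 × 1 = 0.13 points, and a 14-day mean by 0.5 / 14 × 1 = 0.04.

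**Conclusion.** The point holds as a defect of measurement. The primary pain question lacks a recall period and a pain type, its neighbours have a period, and no other section fills the gap. The consequence is mainly avoidable noise in the primary endpoint and in the SD carried forward. It is not a demonstrated bias, and mixing of constructs between hospital and home is a possibility only.

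The size is not known from the documents. If reliability fell from 0.90 to 0.80, the loss would be about 11% of effective sample for one score. For a 4-day mean it would be about 3% with independent errors, and up to 11% if patients hold to their own reading. A larger share of variance from inconsistent reading would cost more, as the range shows. N and alpha are unaffected. The correction is worth making because it is cheap and can only be made in advance.

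**What to change.** Before enrolment, anchor the item to the past 24 hours and to one named pain type. For example: *On average, how would you rate your knee pain over the past 24 hours? (0–10)*. On the first postoperative morning, replace the window with *since surgery*, so that time before the operation is not rated. Ask the identical item each morning in hospital and on every survey, online or by phone, and use only that item for the primary endpoint. State in section 3.7 that the baseline NRS uses it too.

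Average pain is a choice; worst or current pain could be named instead, provided that one is named and kept. The time point or summary for the primary analysis still has to be stated separately, since the rewording does not supply it.

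Cost: a small survey and CRF wording change, with no extra contacts. A 24-hour average may miss brief pain peaks, and at the weekly, day-30 and day-60 surveys it describes one day and not the whole interval.
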